## 6.6. Pharmacodynamic Analysis

Analyses of secondary endpoints relating to ALA and PBG levels are described in Section 6.5.2. In addition, ALA, PBG, and ALAS1 levels will be summarized descriptively at each scheduled visit.

Population PK/PD analyses will be described in a separate population PK/PD analysis plan.

## 6.7. Pharmacokinetic Analysis

Plasma concentrations of givosiran and its major metabolite, AS(N-1)3' givosiran, will be summarized by nominal sampling time.

In patients at East Asian study centers with intense PK sampling, plasma and urine PK parameters of givosiran and AS(N-1)3' givosiran will be determined using non-compartmental methods. PK parameters include maximum plasma concentration ( $C_{max}$ ), time to maximum plasma concentration ( $t_{max}$ ), elimination half-life ( $t_{1/2\beta}$ ), and area under the concentration-time curve (AUC). Other parameters may be calculated, if deemed necessary. PK parameters will be described using summary statistics.

Population PK analysis will be used to describe plasma PK of givosiran and AS(N-1)3' givosiran across all patients. The population PK analysis will be described in a separate modeling and simulation analysis plan.

## 6.8. Safety Analysis

An adverse event (AE) is any untoward medical event associated with the use of a study drug, whether or not it is considered related to the study drug. The primary safety parameter is the AEs that first occurs or worsens after the first dose of study drug. Safety parameters also include vital

signs, ECGs, clinical laboratory assessments, and physical exams. Analyses for safety parameters will be conducted using the Safety Analysis Set.

Time windows for safety data to be analyzed for the 6m-DB period and the entire study including both 6m-DB and OLE periods as well as safety follow-up are described in Section 5.10. All safety data regardless of time windows will be listed and summarized for selected endpoints, i.e. AEs by system organ class (SOC) and preferred term (PT), SAEs by SOC and PT, and selected laboratory parameters.

Subgroup analysis for safety variables may be conducted if deemed appropriate and necessary.

No inferential safety analysis is planned.

### **6.8.1. Adverse Events**

AEs will be classified by the MedDRA coding system (version 21.0 or later) and displayed in tables and data listings using SOC and PT.

AEs will be summarized by the numbers and percentages of patients reporting at least one AE, having at least one AE by primary SOC and PT. A patient with multiple occurrences of an AE will be counted only once in the respective AE category. Patients who report multiple occurrences of the same AE (PT) will be classified according to the most related or most severe occurrence, respectively.

Injection site reaction (ISR) events will be thoroughly summarized. The numbers and percentages of patients reporting at least one ISR event and the numbers and percentages of patients with different ISR symptoms will be summarized. Note that multiple symptoms of a single ISR will not be counted as multiple ISRs. In addition, ISRs will be characterized by injection. The incidence rate of ISR, defined as the number of ISRs divided by total number of injections will also be summarized. If there are multiple ISRs that occur between two consecutive injections, these events are considered caused by the earlier injection and counted as one ISR.

An overall summary of AEs will include the number and percentage of patients with any AE, any AE assessed by the Investigator as related to treatment (possibly related or definitely related), any severe AE, any severe AE related to treatment, any serious AE (SAE), any SAE related to treatment, any AE/SAE of clinical interest; any AE/SAE leading to treatment discontinuation, any study drug related AE/SAE leading to treatment discontinuation, any AE/SAE leading to study withdrawal, any study drug related AE/SAE leading to study withdrawal, and any deaths.

Tabulations by SOC and PT may be produced for the following. The SOC and PT within each SOC will be presented alphabetically.

- All AEs;
- AEs by severity;
- All SAEs;
- AEs related to treatment;
- SAEs related to treatment;
- AEs leading to temporary treatment interruption;

- AEs leading to treatment discontinuation;
- SAEs leading to treatment discontinuation;
- AEs leading to study withdrawal;
- SAEs leading to study withdrawal.

Tabulations by PT in decreasing order in frequency in the givosiran arm will be produced for the following.

- All AEs;
- All SAEs;
- AEs related to treatment;
- SAEs related to treatment;

AEs and SAEs will also be summarized by maximum relationship to study drug and by maximum severity.

AEs mapping to the MedDRA high level term (HLT) of injection site reaction will be summarized by preferred term. AEs mapping to the standard MedDRA query (SMQ) Drug Related Hepatic Disorder will be summarized by SOC and preferred term. Adverse event mapping to a customized Acute Pancreatitis SMQ will be summarized by SOC and preferred term (PT). AEs mapping to the Acute Renal Failure SMQ will be summarized by SOC and PT. AEs mapping to the Anaphylactic Reaction SMQ will be summarized by PT. AEs mapping to the SMQ Malignant or Unspecified Tumors will be summarized by high level term and preferred term. Other SMQs or AE groupings may be evaluated.

AEs mapping to a modified Acute Pancreatitis SMQ were summarized by SOC and PT. This custom SMQ strategy was developed in such a way as to capture more possible pancreatitis cases than the standard MedDRA SMQ. This SMQ included all AEs from the acute pancreatitis SMQ (narrow terms) plus the PTs for lipase increased, lipase abnormal, amylase increased, amylase abnormal, hyperlipasaemia, hyperamylasaemia, pancreatic enzyme abnormality, pancreatic enzymes abnormal, pancreatic enzymes increased.

All AEs collected will be listed along with the information collected on those AEs, e.g. AE relationship to study drug, AE outcome etc. By-patient listings will also be provided for the following: all deaths, all SAEs, and all AEs leading to treatment discontinuation or study withdrawal, all AEs leading to death.

A listing of ISRs will be presented including descriptions, onset and resolution date, severity, treatment given, and event outcome.

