1.3. Study Design Rationale

Data from the Phase 1 Study ALN-AS1-001 in CHE and AIP patients has demonstrated that administration of givosiran resulted in reduction in serum ALAS1 levels, leading to dose-dependent and durable reductions in urinary ALA and PBG. Furthermore, in patients with recurrent attacks (Part C), the reduction in ALA and PBG was associated with significant reductions in porphyria disease activity as indicated in Section 1.2.2.1. Phase 1 (ALN-AS1-001) and Phase 2 (ALN-AS1-002) data have also demonstrated evidence of clinically relevant reduction in the number and severity of porphyria attacks and meaningful improvement in other clinical outcomes in patients with porphyria. Further details of Studies ALN-AS1-001 and ALN-AS1-002 are summarized in the givosiran Investigator's Brochure.

The ENVISION Study (ALN-AS1-003) is a multicenter, multinational Phase 3 study designed to evaluate the efficacy and safety of SC-administered givosiran in patients with AHPs (n=74); the study is comprised of a 1:1 randomized, placebo-controlled double-blind treatment period of 6 months, followed by an OLE period of up to 30 months to evaluate the long-term safety and efficacy of givosiran.

During the 6-month placebo-controlled double-blind treatment period, all patients will receive SC doses of 2.5 mg/kg givosiran or placebo once monthly.

Patients crossing over to the OLE period will receive a dose based on the protocol version upon which they entered the OLE. Patients who crossed over to the OLE period prior to the implementation of amendment 3 (ie, under amendment version 1 or 2) and are receiving a 2.5 mg/kg once monthly givosiran dose will remain on that dose. Upon entry to the OLE period under amendment 3, patients will cross over to receive the 1.25 mg/kg once monthly dose of givosiran, enabling data on this additional dose of givosiran to be generated.

After implementation of amendment 3 and until implementation of amendment 5, patients assigned to the once monthly 1.25-mg/kg treatment group who experience inadequate disease control may be allowed to have their monthly dose increased to 2.5 mg/kg starting at the Month 13 Study Visit (when 6 months of open-label givosiran dosing have been completed at 1.25 mg/kg) based on discussion and agreement by the Investigator and medical monitor, demonstration of tolerability to givosiran, and fulfillment of ALA and clinical activity criteria.

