8.2.9. Other Analyses

The long-term efficacy and safety data of givosiran over the OLE period will be summarized descriptively. Patients who were randomized to placebo and received givosiran at a starting dose of 1.25 mg/kg once monthly during the OLE period (per amendment version 3) will be assessed to characterize the efficacy and safety for the lower dose 1.25 mg/kg once monthly.

Analyses for other exploratory endpoints such as exploratory biomarkers will be detailed in the SAP.

Additional data summaries to help understand any impact of the COVID-19 pandemic on efficacy and safety assessments will be performed, as appropriate.

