### 2.1. Synopsis of Study Design

The ENVISION Study (ALN-AS1-003) is a multicenter, multinational Phase 3 study designed to evaluate the efficacy and safety of givosiran in approximately 74 patients with AHPs; the study is comprised of a 1:1 randomized, double-blind, placebo-controlled period of 6 months, followed by an open-label extension (OLE) period of up to 30 months to evaluate the long-term safety and efficacy of givosiran.

Patients who crossed over to the OLE period prior to the implementation of the protocol amendment 3 (i.e., under amendment version 1 or 2) and are receiving a 2.5 mg/kg once monthly givosiran dose will remain on that dose. Upon entry to the OLE period under amendment version 3, patients will cross over to receive a 1.25 mg/kg once monthly dose of givosiran. Starting at Month 13 (when 6 months of open-label givosiran dosing have been completed), patients in the once monthly 1.25 mg/kg treatment group who experience inadequate disease control may have their monthly dose increased to 2.5 mg/kg, upon discussion and agreement by the Investigator and medical monitor and demonstration of tolerability to givosiran and if ALA criteria are met (urine ALA levels (mmol/mol Cr) are not stably maintained  $\leq$ ULN or are inducible).

The study design schema is presented in [Figure 1](#).

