#### 4. PATIENT POPULATION

The populations (analysis sets) are defined as follows:

- Full Analysis Set (FAS): All randomized patients who received at least one dose of study drug. Patients will be grouped by their randomly assigned treatment group (i.e. as randomized).
- AIP patients in the Full Analysis Set (FASAIP): All randomized AIP patients (with identified mutation in the *HMBS* gene) who received at least one dose of study drug. Patients will be grouped by their randomly assigned treatment group (i.e. as randomized).
- Per Protocol Analysis Set (PPS): All randomized AIP patients (with identified mutation in the *HMBS* gene) who received at least 4 doses (>60%) of study drug during the 6-month double-blind period, were followed for collection of attack data through 6 months ( $\geq 162$  days) and did not experience major protocol deviations that may impact the primary efficacy results (e.g., not meeting the key inclusion/exclusion criteria). Patients will be analyzed according to their randomly assigned treatment group.
- Safety Analysis Set (SAS): All patients who received at least one dose of study drug, grouped according to the treatment actually received.
- PK Analysis Set: All patients who received at least one dose of study drug and have evaluable PK data contributing to the estimation of PK parameter.
- PD Analysis Set: All patients who received at least one dose of study drug and who have baseline and at least one post-dose urine sample for the determination of ALA or PBG.
- All Givosiran Treated Set: All patients who received at least one dose of givosiran, including patients who took givosiran during the 6m-DB period and patients who first took placebo during the 6m-DB period and switched to givosiran during the OLE period.

Both FAS and FASAIP will be used to evaluate efficacy endpoints. The primary endpoint will also be analyzed using the Per Protocol Set. Safety during the 6m-DB period will be analyzed using the Safety Analysis Set. The PK and PD Analysis Sets will be used to conduct PK and PD analyses, respectively. The All Givosiran Treated Set will be used to summarize long-term efficacy and safety data during givosiran treatment. See Section 5.10 for details. Number of patients included in all analysis sets will be provided.

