The start day of the OLE period is defined as the day when the first dose of the OLE period is administered. The assessments collected or AEs with onset after the administration of the first dose of the OLE period will be included in the OLE period. When assessments or AE onset dates are exactly the first OLE dose date with time missing, the records will be included in the OLE period.

- **During Givosiran Treatment**

For all patients who received at least one dose of givosiran, data will be summarized for the “during givosiran treatment” period, defined as below.

- 1) For patients who received givosiran in the 6m-DB period, all assessments collected after the first dose of givosiran during the entire study including both the 6m-DB and OLE periods (if available) will be included in the “during givosiran treatment”.
- 2) For patients who received placebo in the 6m-DB period and switched to givosiran in the OLE period, all assessments collected after the first dose of givosiran in the OLE period will be included in the “during givosiran treatment”.
- 3) For patients who discontinued givosiran treatment during the 6m-DB period, the data handling will follow the same rules as discussed above for “6m-DB period”. For discontinuation in the OLE period, assessments within 28 days of the last dose of givosiran will be included in summaries. For ongoing patients, all data are included.

Selected efficacy parameters will be summarized over the entire study including the 6m-DB and OLE periods for all patients to show the trajectory changes comparing the placebo experience versus the givosiran experience, for example, summary of creatinine normalized urinary ALA by visit. In these summaries, the treatment groups are “Givosiran” or “Placebo” based on randomization during the 6m-DB period.

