### **Treatment sequence**

Patients are assigned to receive either 2.5 mg/kg or 1.25 mg/kg once monthly dose of givosiran upon entry to the OLE period through the end of Month 12 (At Month 13, patients on 1.25 mg/kg once monthly dose may receive a dose adjustment). After sufficient data are collected during the OLE period, summaries for the All Givosiran Treated Set will be provided by the following subgroups:

- Givosiran/Givosiran:
  - Givosiran 2.5 mg/kg/Givosiran 2.5 mg/kg: all patients who received givosiran 2.5 mg/kg in 6m-DB and OLE periods.
  - Givosiran 2.5 mg/kg/ Givosiran 1.25 mg/kg: all patients who received givosiran 2.5 mg/kg in the 6m-DB period and givosiran 1.25 mg/kg in the OLE period;
  - Overall: all patients who received givosiran at any dose level in the 6m-DB, including patients who discontinued during 6m-DB and did not receive dose in OLE.
- Placebo/Givosiran:
  - Placebo/Givosiran 2.5 mg/kg: all patients who received placebo in the 6m-DB period and givosiran 2.5 mg/kg in the OLE period;
  - Placebo/ Givosiran 1.25 mg/kg: all patients who received placebo in the 6m-DB period and givosiran 1.25 mg/kg in the OLE period.
  - Overall: all patients who received placebo during the 6m-DB period and switched to givosiran at either dose level in the OLE period;
- Givosiran 2.5 mg/kg: all patients who received givosiran 2.5 mg/kg in either 6m-DB or OLE periods;
- All Givosiran: all patients who received any dose of givosiran during either 6m-DB or OLE period.

To assess the effect of givosiran 2.5 mg/kg and 1.25 mg/kg on ALA reduction separately, for the two subgroups Placebo/Givosiran 2.5 mg/kg and Placebo/Givosiran 1.25 mg/kg, Wilcoxon signed rank test will be conducted for intra-patient comparison on the medians over the 6m-DB period versus the OLE period, Month 3 vs. Month 9, and Month 6 vs. Month 12, when sufficient data are collected during the OLE period.

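### While the open-label extension is ongoing, crude AE percentages by dose sequence are confounded with follow-up time

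*SAP*

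**What the plan says.** **Dose in the extension.** It was not randomized. Protocol 1.3 states: "Patients crossing over to the OLE period will receive a dose based on the protocol version upon which they entered the OLE". SAP 2.1 gives the detail: patients who crossed over under amendment 1 or 2 and "are receiving a 2.5 mg/kg once monthly givosiran dose will remain on that dose", while those entering under amendment 3 start at 1.25 mg/kg.

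**Population and groups.** SAP 4: "The All Givosiran Treated Set will be used to summarize long-term efficacy and safety data during givosiran treatment". Under the Treatment sequence heading of SAP 5.10, "summaries for the All Givosiran Treated Set will be provided by the following subgroups": Givosiran 2.5/2.5, Givosiran 2.5/1.25, Placebo/2.5, Placebo/1.25, and pooled groups. The sequence split therefore applies to safety.

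**Follow-up counted.** SAP 5.8 uses a calendar cutoff for analyses made while the study continues. SAP 5.10 says of givosiran treatment: "For ongoing patients, all data are included". For patients randomized to givosiran, that period starts in the double-blind phase; for placebo crossovers, it starts at the first open-label dose.

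**Measure.** SAP 6.8.1: "AEs will be summarized by the numbers and percentages of patients reporting at least one AE". The one measure there with an exposure denominator is for injection site reactions: "The incidence rate of ISR, defined as the number of ISRs divided by total number of injections will also be summarized". I found no person-time rate, time-to-event summary or common follow-up window for AEs or SAEs.

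**Purpose.** Protocol 8.2.9 says that placebo patients who start the extension at 1.25 mg/kg "will be assessed to characterize the efficacy and safety for the lower dose 1.25 mg/kg once monthly".

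**The concern.** The proportion of patients with at least one event rises with time observed. Here time observed is tied to dose, because the earlier entrants started at 2.5 mg/kg and the later ones at 1.25 mg/kg. At a calendar cut during the extension, a side-by-side table of percentages mixes any dose effect with length of follow-up.

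A second imbalance is built into the design. Givosiran/Givosiran includes the 6 double-blind months and Placebo/Givosiran does not, so the former has about 6 months more givosiran exposure, and this persists at final lock.

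At stake is the description of 1.25 mg/kg safety that Protocol 8.2.9 promises. The plan already takes care over time for other endpoints. In SAP 5.10, attacks and hemin use are annualized, with at least 85 days of open-label follow-up required for the intra-patient rates, and ALA is compared at matched visits (Month 3 with 9, Month 6 with 12). Protocol 1.4 compares the two doses on benefit over the first 6 open-label months in former placebo patients. AEs get nothing equivalent.

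**Working it through.** The plan states no figure for this point, so there is nothing to reproduce. The check asks what the planned measure shows when the two doses carry the same risk.

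**1. Plausible follow-up gap (assumption).** The documents give neither implementation dates nor individual entry dates. Suppose extension entry is spread evenly between two dates:
- 21 Feb 2018, which is 168 days after the original protocol of 06 Sep 2017;
- 26 Feb 2019, which is 168 days after SAP amendment 1 of 11 Sep 2018, assuming enrolment had closed by then.

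Split at amendment 3 (21 Sep 2018), the two windows are 212 and 158 days. The mean gap is (212/2 + 158/2)/30.44 = 6.1 months. I treat 6 months as roughly the upper limit and show 1, 3 and 6.

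**2. Equal constant hazards (assumption).** Let r be the six-month risk and λ = −ln(1 − r)/6 per month. The crude percentage at t months is 1 − exp(−λt). For r = 20%, λ = 0.0372. With the 1.25 mg/kg group at 6 months:

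| Six-month risk | 1.25 mg/kg, 6 months | 2.5 mg/kg, 7 months | 9 months | 12 months | Ratio |
|---|---|---|---|---|---|
| 5% | 5.0% | 5.8% | 7.4% | 9.8% | 1.16–1.95 |
| 20% | 20.0% | 22.9% | 28.4% | 36.0% | 1.15–1.80 |
| 50% | 50.0% | 55.5% | 64.6% | 75.0% | 1.11–1.50 |
| 90% | 90.0% | 93.2% | 96.8% | 99.0% | 1.04–1.10 |

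The true ratio is 1 throughout. The relative distortion is largest for uncommon events and nearly gone for near-universal ones.

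**3. Later cuts.** At r = 20% with a 6-month gap, 18 against 24 months gives 48.8% against 59.0% (ratio 1.21). If both dose groups complete 29 months, each shows 66.0% and the between-dose artefact is zero.

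**4. Givosiran/Givosiran against Placebo/Givosiran.** Protocol 4.2 allows up to 35 and up to 29 months of givosiran respectively. At r = 20%: 1 − 0.8^(35/6) = 72.8% against 1 − 0.8^(29/6) = 66.0%. This gap remains at final lock.

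**5. Events clustered early.** The amendment 6 rationale says that transaminase elevations arose mainly 3 to 5 months after starting givosiran. Assume a hazard confined to months 3–5 with cumulative risk 15%. With the lower-dose group at month 4 and the other at month 5 or later, the table shows 1 − 0.85^0.5 = 7.8% against 15.0%. Once both groups have passed month 5, both show 15.0%.

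**6. What the remedies do.** Under constant hazards at r = 20%, both groups show 12 × 0.0372 = 0.446 first events per patient-year, and 20.0% in a common six-month window. For early-clustered events the person-time rate can err. Assume 15% risk in both groups, all events at month 4, and follow-up of 8 against 13 months:
- 8 months: mean time at risk 0.85 × 8 + 0.15 × 4 = 7.4 months; 0.15/(7.4/12) = 24 per 100 patient-years.
- 13 months: 0.85 × 13 + 0.15 × 4 = 11.65 months; 0.15/(11.65/12) = 15 per 100 patient-years.

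That is a spurious ratio of about 1.6 against the group with shorter follow-up. The common window avoids it.

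**The case against.** The case on the other side has real weight.

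- **The main safety comparison is unaffected.** It is the randomized 6-month period, where crude percentages are appropriate. Long-term safety is descriptive, and SAP 6.8 plans no inferential safety analysis. This stands and limits the importance of the point.
- **Readers can see the exposure.** SAP 6.4 summarizes days of exposure and number of administrations, and all AEs are listed. That discloses the imbalance but does not adjust the percentages for it.
- **The gap closes at hard lock.** The planned maximum extension is the same for both dose groups, so a reader who infers distortion at every data cut goes too far. Some gap could remain if treatment ended by calendar date, since Protocol 4.1 lets commercial availability end it.
- **The direction is not uniform.** A reader might infer that the lower dose always looks safer. But patients on 1.25 mg/kg could be escalated from Month 13 and were generally escalated under amendment 5 (Protocol 6.2.3.4); the amendment 5 rationale reports requests for 14 of 37 (38%). SAP 5.10 has no rule to censor at dose change, so events on 2.5 mg/kg can be counted under a 1.25 mg/kg sequence. The Givosiran 2.5/1.25 group also includes double-blind time on 2.5 mg/kg.
- **Dose decisions.** A reader might infer that biased AE percentages drove the later dose change. The documents do not show this. Protocol 1.4 bases the between-dose argument on attacks, hemin use, ALA and PBG over the first 6 open-label months in former placebo patients.

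**Conclusion.** The point holds for calendar cuts made while the extension is ongoing. AE and SAE percentages by dose sequence then mix risk with follow-up, because open-label dose followed date of entry and the plan neither adjusts for exposure nor sets a common window. Givosiran/Givosiran against Placebo/Givosiran has the same problem by design, including at final lock.

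The size rests on assumptions: hazard, its shape, and the follow-up gap are not in the documents. At a 20% six-month risk with equal constant hazards, the spurious difference at a 6-month follow-up is about 3, 8 or 16 percentage points for gaps of 1, 3 or 6 months. It is small for near-universal AEs, largely absent for events confined to months 3–5 once both groups have passed that point, and zero between doses if both complete the same extension length.

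This is a cheap improvement to a descriptive display. It does not affect the randomized comparison and is not evidence that any dose decision was wrong.

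**What to change.** In SAP 6.8.1:

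1. **Primary between-dose display.** Base any AE or SAE comparison between doses on the common first 6 open-label months (Month 6 to Month 12), before escalation was allowed at Month 13. Either restrict it to patients who entered early enough to have that follow-up by the cutoff, defined by entry date so that early discontinuations stay in, or censor at the cutoff and report cumulative incidence. Make the main comparison Placebo/Givosiran 2.5 mg/kg against Placebo/Givosiran 1.25 mg/kg, since only these patients start givosiran at extension entry.
2. **Longer-term supplement.** For the All Givosiran Treated Set and its sequence subgroups, add patients with the event per 100 patient-years to first event. Censor follow-up at dose change so that events on 2.5 mg/kg are not counted under a 1.25 mg/kg sequence.

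The cost is one windowed table, one extra column and a censoring rule, with no new data. The windowed table says nothing about later events, and person-time rates can mislead for early-clustered events, which is why the common-window table should be primary. The dose groups remain non-randomized after either change.
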